#### 6.2.1 Anticipated adverse device effects

Anticipated adverse device effects are those associated with surgical implantation. The H1 hip resurfacing has been designed and manufactured to comply with the Essential Requirements of the Medical Devices Directive. The H1 device will be implanted by experienced surgeons with a device specific instrument set. Nevertheless, possible risks remain. Adverse device effects include:

- Pain
- Reduced Function (including squeaking)
- Fracture (Implant fracture, femoral fracture, explantation related fracture)
- Implant loosening

These risk categories also reflect the clinically highlighted safety risks from the clinical evaluation report. The clinical outcomes, which do not feature on these risk categories, are:

- Dislocation: the probability of occurrence of dislocation is extremely low
- Metallosis: the probability of occurrence of metallosis is extremely low

#### 6.2.2 Risks associated with participation in the clinical investigation

As the surgery undertaken in this study is the same as that which a patient not partaking in this study would receive, the risks of participation are those associated with hip replacement surgery and anaesthesia:

- Adverse events associated with anaesthesia (cardiac, pulmonary, neurological, gastrointestinal, urinary)
- Bleeding, haematoma, wound suture dehiscence
- Superficial or deep infection of the wound or hip joint
- Deep vein thrombosis
- Transient nerve palsy
- Mortality
- 6.2.2.1 Possible interactions with concomitant medical treatments

There are no foreseen possible interactions with concomitant medical treatments.

#### 6.3 Risk mitigation

Risk control measures have been verified through pre-clinical testing of the H1 device and risks have been reduced as far as possible, using the following techniques in the order in which they are presented:

- 1. Inherent safety by design;
- Protective measures in the medical device itself or in the manufacturing process;
- 3. Information for safety (labelling, instructions for use (IFU), etc.);

Wherever possible risks have been mitigated through the design of the device.

# 6.4 Overall risk benefit profile of the H1 device

The H1 device has been designed for reducing pain and restoring function to patients with arthritis of the hip. The potential benefits of the H1 device in comparison to the THR and the gold standard metal-on-metal hip resurfacing (The Birmingham Hip Resurfacing – BHR) clearly out-weigh the residual risks in quantity. There are no 'high' residual risks, which have not been accounted for in the clinical evaluation. By weighing the clinically evidenced risks against the clinically evidenced benefits, it is clear that the H1 has the potential to provide a superior solution to both THR and BHR, assuming that the patient indications are correct. The risk benefit profile of the H1 HRA has been presented based on clinical evaluation and design verification. Further clinical data may be required to fully verify the design. In its current status the benefits of the H1 hip resurfacing outweigh the risks.

For the full risk management process, and a deeper discussion of the risk-benefit analysis, please refer to the Risk Management Plan and the Risk Management Report [34, 36].

# **PART B:** INVESTIGATION DESIGN

# 7 Investigation Objectives and Hypotheses

# 7.1 Objectives

The investigational device – the H1 HRA – is a cementless ceramic-on-ceramic hip resurfacing arthroplasty. It meets all the Essential Requirements of the Medical Devices Directive, with the exception of clinical data to support its design. The principles of ceramic-on-ceramic hip replacement, hip resurfacing and cementless fixation in joint replacement have been proven in many long-term studies.

Therefore, this clinical investigation is being conducted to verify the short-, mid- and long-term **safety** and **efficacy** of the H1 HRA, in relation to its design features.

#### 7.1.1 Primary Objective – Safety and Efficacy Study

The *primary objective* is to confirm the **safety** and **efficacy** of the H1 hip resurfacing prosthesis by demonstrating non-inferiority of the cumulative percent success in subjects implanted with the H1 hip resurfacing compared to a literature reference rate of 98.6% cumulative survivorship without revision for any reason of the Birmingham hip resurfacing (BHR) at 1 year, 97.6% survivorship at 3 years, 96.5% survivorship at 5 years and 93% cumulative survivorship at 10 years (Australian Joint Registry AOAAJR annual report 2015)[19].

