# 8 Investigation Design and Endpoints

- 8.1 General
- 8.1.1 Type of investigation

This is a multi-centre, prospective, non-randomized, observational study to evaluate the clinical outcome of the H1 hip resurfacing implant.

In order to evaluate the safety of the new device, the study will be subdivided in a shortterm safety study and a long-term safety and efficacy study. The safety study (Cohort 1A – 20 patients) will record complication rate, toxicology and radiological assessment. Cohort 2 will consist of the remaining patients due to undergo a primary hip arthroplasty. Owing to the observation of femoral crush fractures in the first cases undertaken, a second safety cohort will be undertaken - Cohort 1B. Cohort 1B will consist of a further 46 patients.

The data from the study will also be used to compile a report for submission to the manufacturer's notified body in order to obtain a CE marking for the H1 HRA. If the H1 receives a CE mark at this stage, an amendment will be placed to the main REC and the competent authority in order to continue with the study as a post-market surveillance of a CE Marked device as per assessments listed in the schedule of procedures. If the CE marking is not obtained at that point, the study will continue as per protocol.

See the flow diagrams in Figure 1 to Figure 3 for a graphical explanation of the investigation plan.

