# 10 Statistical Methods

## **10.1** Hypotheses and Sample Size

#### 10.1.1 Primary Objective - Safety and Efficacy Study

A total of 250 cases will be enrolled into the study at the 9 investigation sites.

When 250 cases are enrolled from all sites, enrolment will be stopped, regardless of the number contributed from each site.

The sample size is calculated based on the non-inferiority of the study device; the following hypotheses will be tested to test the difference in success rate (defined in section 2) of the study device with the reference rate with non-inferiority margin,  $\delta > 0$ :

$$H_0: \pi_0 - \pi \ge \delta$$
$$H_a: \pi_0 - \pi < \delta$$

Where  $\pi$  is success rate of study device and  $\pi_0$  is reference rate, respectively and  $\delta = 5\%$ . For these hypotheses, rejection of the null hypotheses will imply non-inferiority of the study device compared to the reference rate.

For the above hypotheses, the sample size for a specified  $\alpha$  and power  $(1 - \beta)$  is given by:

$$n = \frac{(z_a + z_b)^2 (\pi (1 - \mu))}{(\mu_0 - \mu - \delta)^2}$$

Where  $\delta$  is the non-inferiority margin and non-negative number [43].

The success rate for the study device is unknown for this population but there is no reason to believe that it would be less than reference rate of 93% (95%CI: 92.4-93.6%) [19]. Therefore, a conservative success rate of 93% of the study device is used at 10 years study.

The non-inferiority margin  $\delta$  of 0.05 is chosen in the study [43]. 225 subjects are required to achieve  $100(1 - \beta) \% = 80\%$  power to detect non-inferiority at the Significance level of  $\alpha = 0.05$  (single-sided hypothesis). Based on the experience, allowing 10% of the patients lost to follow up by the end of 10 years, a sample size of 250 cases are needed in this study. Therefore, 250 cases will be enrolled in the study (20 cases minimum to be recruited at each site; in case one centre is not able to recruit the allocated target size of cases, numbers can be picked up by the other centres).

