# 10.2 Statistical Analysis

A non-inferiority test of the cumulative percent success (defined in section 2) in subjects implanted with the H1 hip resurfacing compared to a literature reference rate will be the primary test of efficacy in this study. The null hypothesis is H0:  $\pi_0 - \pi \ge 0.05$  and the alternative hypothesis is Ha:  $\pi_0 - \pi < 0.05$ .

Primary and secondary outcomes will be evaluated using listings and summary statistics. A confidence interval of 95% will be calculated for proportions and averages. Improvement in pain and function will be analysed using parametric (t-test) or non-parametric (Wilcoxon Rank tests) as appropriate. A Kaplan Meier survival estimate will be calculated in this study. For the survivorship analyses, revisions are defined as revision for any reason. Prognostic factors will be adjusted, if necessary, using parametric or non-parametric analyses (log Rank; Cox regression). All statistical analyses and calculation of confidence intervals will be performed using appropriate statistical software packages.

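### The primary objective lists non-inferiority at 1, 3, 5 and 10 years, but the only margin (5 points) is sized for 10 years, and no time point is named for the primary test

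*Protocol*

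**What the plan says.** Protocol section 7.1.1 defines the primary objective as demonstrating non-inferiority of cumulative percent success "compared to a literature reference rate of 98.6% cumulative survivorship without revision for any reason" for the BHR, and continues "at 1 year, 97.6% survivorship at 3 years, 96.5% survivorship at 5 years and 93% cumulative survivorship at 10 years". All four rates sit in the same sentence with equal standing.

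Section 10.1.1 states the hypotheses with one margin, which "of 0.05 is chosen in the study". No other margin appears in the protocol. The sizing uses one time point: "a conservative success rate of 93% of the study device is used at 10 years study". The significance level is 0.05 ("single-sided hypothesis"), with 80% power, 225 evaluable subjects and 250 enrolled.

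Section 10.2 says that the non-inferiority test "compared to a literature reference rate will be the primary test of efficacy in this study". That is one rate and one test, with no year attached. Hypothesis 1 in section 7.2 names no time point either.

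Section 8.3.3 plans interim analyses at 6 months and annually to describe safety and efficacy, with the final analysis at 10 years. Table 1 (section 8.3.4) lists survivorship among the data for those interim reports. Section 8.1.1 says that study data will go into a report for "submission to the manufacturer's notified body in order to obtain a CE marking for the H1 HRA".

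**The concern.** The objective and the test do not match. The objective asks for non-inferiority at four times. The statistical section supplies a margin and a sample size for one, and does not say which comparison decides the objective.

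The gap matters because the meaning of a fixed 5-point margin depends on the reference rate. Against 7% revised at 10 years it is a moderate allowance. Against 1.4% revised at 1 year it is several times the reference itself. Someone writing a 1-year report could take the 1-year rate from 7.1.1 and the margin from section 10 and state non-inferiority to BHR on the primary endpoint. Nothing in the protocol forbids this, and the test would discriminate poorly. Early failure is also a live question for this device: section 3.1 records femoral crush fractures, first seen as unexplained femoral head movement in the 6-month data.

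**Working it through.** **Inputs.** Reference survivorship of 98.6, 97.6, 96.5 and 93% comes from section 7.1.1, so the reference revision rates are 1.4, 2.4, 3.5 and 7.0%. The margin of 0.05, one-sided alpha of 0.05, 80% power, 225 evaluable and 250 enrolled come from section 10.1.1.

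**The plan's own figure.** With the variance taken at the margin under the null and at 93% under the alternative:

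n = [1.645 × √(0.88 × 0.12) + 0.842 × √(0.93 × 0.07)]² / 0.05² = 224.6, so 225; and 225 / 0.90 = 250.

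This reproduces the stated size and confirms that it belongs to the 10-year comparison alone.

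**Revision rate at the margin.** This is the reference revision rate plus 5 points; the ratio is that limit divided by the reference.

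| Year | Reference revised | Limit | Ratio |
|---|---|---|---|
| 1 | 1.4% | 6.4% | 4.57 |
| 3 | 2.4% | 7.4% | 3.08 |
| 5 | 3.5% | 8.5% | 2.43 |
| 10 | 7.0% | 12.0% | 1.71 |

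**Chance of passing.** The exact test passes when the number of revisions is at most c, the largest count for which P(X ≤ c), with X binomial at the limit, is no more than 0.05. The pass probability at a doubled rate is P(X ≤ c) with X binomial at twice the reference. Follow-up is taken as complete and hips as independent.

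| Year | True rate (2 × reference) | c, n = 225 | Pass, n = 225 | c, n = 250 | Pass, n = 250 |
|---|---|---|---|---|---|
| 1 | 2.8% | 8 | 82% | 9 | 83% |
| 3 | 4.8% | 9 | 36% | 11 | 46% |
| 5 | 7.0% | 12 | 20% | 13 | 16% |
| 10 | 14.0% | 18 | 0.4% | 21 | 0.5% |

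At 1 year a tripled rate (4.2%) passes 39% of the time at either size.

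**Sensitivity to the test rule (1 year, doubled rate).** A Wald rule gives 90-91%. An exact test at one-sided 0.025 gives 70-73%.

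**Sensitivity to the number of hips.** The protocol does not say how many hips an early report would hold, so these sizes are assumptions. With the exact one-sided 5% test at 1 year, a doubled rate passes 15% of the time with 66 hips (Cohorts 1A and 1B, 20 + 46), 47% with 100, 59% with 150 and 67% with 200. With 66 hips, a device equal to the reference passes only 39% of the time.

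**Would a scaled early margin work?** Holding the 10-year ratio (12/7) at 1 year puts the limit at 1.4% × 12/7 = 2.4%, a margin of 1.0 point. A device equal to the reference would then pass about 13-32% of the time with 225 to 250 hips (exact and score rules). For 80% power:

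n = [1.645 × √(0.976 × 0.024) + 0.842 × √(0.986 × 0.014)]² / 0.01² ≈ 1,230.

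Scaling the margin is not workable at this sample size.

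**The case against.** The strongest reply is that only one test was ever meant. The margin is introduced in a calculation built on 93% at 10 years, section 10.2 speaks of one reference rate and one primary test, section 8.3.3 presents the interim analyses as descriptive, and Table 1 lists survivorship as data with no test attached. This largely stands: a reader might infer from 7.1.1 that the 5-point test is run at all four times, and no section says that. But no section confines the test to 10 years either, and 7.1.1 still places the early rates inside a non-inferiority objective.

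A reader might also infer an inflated type I error from four tests at 5%. The documents do not support that as stated. If all four comparisons had to succeed, the error would not be inflated. It would be inflated only if any one sufficed, and the protocol says neither.

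Nor do the documents show that an early non-inferiority claim is nearly guaranteed or bound for the notified body. The high pass rate is specific to 1 year with near-complete follow-up. Sections 8.1.1 and 19.1 do not date the CE-mark report or say that it will carry a non-inferiority conclusion. Early safety decisions rest on the reviews in sections 8.3.1, 8.3.2 and 18, not on this test.

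A statistical analysis plan might name the time point. That would not remove the mismatch, because the objective, hypotheses and margin are all stated in the protocol.

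**Conclusion.** The point holds as an unresolved mismatch between section 7.1.1 and section 10, not as proof that four tests are planned. The protocol should settle it, because the reading it leaves open is a weak one: at 1 year the 5-point margin sits at 4.6 times the reference revision rate, and a doubled rate would pass about 82-83% of the time. The problem shrinks with time, to 36-46% at 3 years, 16-20% at 5 years and under 1% at 10 years, where the margin does the job it was sized for.

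These figures assume 225 to 250 independent hips with complete follow-up and an exact one-sided 5% test. Censoring and bilateral hips would shift them somewhat, and fewer hips would lower the 1-year figure.

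**What to change.** In sections 7.1.1 and 10.2, state that the 10-year comparison (reference 93%, margin 5 points) is the only confirmatory non-inferiority test. State also that survivorship at 1, 3 and 5 years will be reported descriptively, as the Kaplan-Meier estimate with its 95% interval beside the reference rate, with no claim of non-inferiority. The early rates can stay in 7.1.1 as benchmarks once they are labelled in that way.

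The cost is a wording amendment. Sample size, visits and the content of the interim reports do not change. The sponsor gives up early non-inferiority claims. Keeping such claims with a margin scaled to the early rates is not recommended, given the 13-32% power at 1 year shown above.

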#### 7.1.2 Secondary Objectives

#### **Preliminary Safety Study**

In the first cohort of 20 patients (Cohort 1A), the **safety** of the H1 device will be determined via assessment of complication rate, toxicology and CT assessment. The *secondary objective* is to demonstrate superiority of the ceramic-on-ceramic H1 hip resurfacing prosthesis with its metal-free articulation compared to MoM hip resurfacing in the absence of metal ion release.

#### Second Safety Study

In a second cohort of 46 patients (Cohort 1B), the **safety** of the H1 device will be determined via assessment of complication rate, toxicology (first 14 patients only) and CT assessment. The *secondary objective* is to demonstrate superiority of the ceramic-on-ceramic H1 hip resurfacing prosthesis with its metal-free articulation compared to MoM hip resurfacing in the absence of metal ion release.

#### Safety and Efficacy Study

Additional goals are to demonstrate non-inferiority of the ceramic-on-ceramic H1 hip resurfacing prosthesis compared to hip resurfacing and total hip arthroplasty with regard to patient reported outcome measures, objective clinical and functional outcomes, and radiological assessment at each follow up visit.

Data collected during this study may also be used for other orthopaedic research into the genesis of disease and the effectiveness of treatment in the MSk Lab at Imperial College London. The investigation subjects will be split into two cohorts.

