#### **Investigation objectives**

The *primary objective* is to confirm the **safety** and **efficacy** of the H1 hip resurfacing prosthesis by demonstrating non-inferiority of the cumulative percent success in subjects implanted with the H1 hip resurfacing compared to a literature reference rate of the Birmingham hip resurfacing (BHR).

The *secondary objective* is to demonstrate superiority of the ceramic-on-ceramic H1 hip resurfacing prosthesis with its metal-free articulation compared to MoM hip resurfacing in the absence of metal ion release. Additional goals are to demonstrate non-inferiority of the ceramic-on-ceramic H1 hip resurfacing prosthesis compared to hip resurfacing with regard to patient reported outcome measures, objective clinical and functional outcomes, and radiological assessment.

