# 7.2 Hypotheses

It is hypothesised that:

- 1. The H1 will demonstrate non-inferiority in terms of survivorship compared to the BHR
- 2. The H1 will be demonstrated to be superior in terms of toxicology compared to the BHR

Please refer to Section 10 for more details regarding the null hypotheses and sample size calculations.

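### The goal of demonstrating non-inferiority on PROMs, function and radiology cannot be answered by the analysis the protocol states, and its comparators and visits are not consistent

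*Protocol*

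**What the plan says.** The goal appears twice. In Section 7.1.2, under the Safety and Efficacy Study, it reads "Additional goals are to demonstrate non-inferiority of the ceramic-on-ceramic H1 hip resurfacing prosthesis compared to hip resurfacing and total hip arthroplasty", and the sentence goes on to patient-reported outcome measures, "objective clinical and functional outcomes, and radiological assessment at each follow up visit". In the synopsis, under Investigation objectives, the same goal is set out as "compared to hip resurfacing with regard to patient reported outcome measures" and the other two outcome groups. There, total hip arthroplasty (THA) is not named and no visits are given.

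The synopsis describes the study as non-randomised, and Section 8.2.1 states that all patients receive the H1.

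Section 7.2 lists two hypotheses. One is "The H1 will demonstrate non-inferiority in terms of survivorship compared to the BHR". The other is superiority in toxicology. It refers to Section 10 for the null hypotheses and sample sizes.

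For outcomes in general, Section 10.2 says: "Primary and secondary outcomes will be evaluated using listings and summary statistics" and "A confidence interval of 95% will be calculated for proportions and averages". The only test it names for the outcomes at issue is: "Improvement in pain and function will be analysed using parametric (t-test) or non-parametric (Wilcoxon Rank tests) as appropriate".

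**The concern.** To demonstrate non-inferiority is to make an inferential claim about a comparator. It needs something to compare with, a value for it, and a limit on how much worse is acceptable. The protocol states the aim for two comparators and three groups of outcomes, includes neither comparator in the study, and names a test of a different question. Rejecting the hypothesis of no improvement shows that patients gained after surgery. It does not show that they gained as much as they would have with a metal-on-metal resurfacing or a THA.

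The protocol gives this comparison some weight. Section 8.1.3 notes that the threshold for revising a resurfacing may be low, and for that reason treats the secondary endpoints and the comparison with metal-on-metal resurfacing and THA as an important discriminator. Section 5.2 says that the H1 must not be inferior in overall safety or performance to conventional hip replacement or the Birmingham device. The data go into a CE-marking report (Sections 8.1.1 and 19.1). A reader of that report could look for a non-inferiority result that the stated analysis cannot supply.

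**Working it through.** **1. What the protocol gives for each objective**

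| Outcome | Hypothesis (7.2) | Reference | Margin or sample size | Analysis stated |
|---|---|---|---|---|
| Revision | Non-inferiority | 93% at 10 years (7.1.1, 10.1.1) | Margin 5%; 225 evaluable, 250 enrolled (10.1.1) | Non-inferiority test, Kaplan-Meier (10.2) |
| Metal ions | Superiority | Historical mean cobalt 1.8 µg/L, SD 1.2 (10.1.2) | 14 per group, 20 included (10.1.2) | Difference in mean cobalt (10.1.2) |
| PROMs, clinical/functional, radiology | None | None | None | Summary statistics, 95% intervals, test of improvement in pain and function (10.2) |

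For the first two rows the protocol itself supplies what a comparison needs. For the third it states the aim and none of these elements. It names no test for radiology.

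**2. The protocol's own sample size belongs to the first row only**

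Inputs from 10.1.1: success rate 0.93, reference 0.93, margin 0.05, one-sided 5%, power 80%, loss 10%. With the null variance (success rate 0.93 − 0.05 = 0.88) in the alpha term:

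n = [(1.645 × √(0.88 × 0.12) + 0.842 × √(0.93 × 0.07)) / 0.05]² = 224.6, so 225; and 225 / 0.90 = 250.

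This reproduces the stated figures. (The formula as printed, with the variance at 0.93 only, gives 161; that is a separate matter.) The calculation concerns revision and does not carry over to scores, function or radiographs.

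**3. The two questions are different**

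Let μ be the mean score with the H1 at a visit, b the mean before surgery, μ_ref the comparator's mean and m the margin, with higher scores better.

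- Improvement test: the null hypothesis is μ − b = 0.
- Non-inferiority: the null hypothesis is μ_ref − μ ≥ m.

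The first contains neither μ_ref nor m, so rejecting it leaves the second undecided. The planned 95% interval for a mean could address the second, but only once μ_ref and m are fixed.

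**4. Why no size can be attached**

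The protocol gives no SD, reference or margin for these outcomes. For illustration only, assume one group compared with a fixed reference, true mean equal to that reference, one-sided 2.5% (to match a 95% interval), and 225 independent evaluable hips. The required number for 80% power is n = [(1.96 + 0.842) / m]², and power with 225 is Φ(15m − 1.96), with m in SD units.

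| Assumed margin (SD) | n for 80% power | Power with 225 |
|---|---|---|
| 0.1 | 785 | 32% |
| 0.2 | 197 | 85% |
| 0.3 | 88 | 99% |
| 0.5 | 32 | >99.9% |

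Whether the study could support such a claim thus turns on a figure that the protocol does not give.

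**5. Visits and comparators**

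- Radiographs: Section 8.3.3 plans only clinical and functional assessment at 6 months and 7 years, and Table 4 shows no Cohort 2 radiographs at those visits.
- Treadmill gait: UK sites only, after surgery at years 1 and 5 (Sections 11.3.4 and 11.4).
- Comparators: Section 7.1.2 names hip resurfacing and THA; the synopsis names hip resurfacing.

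A goal set for each follow-up visit therefore cannot be met for radiology or gait on the protocol's own schedule.

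**The case against.** The strongest reply is that Section 10.2 offers more than the improvement test. It plans 95% intervals for means and proportions, and an interval is the usual tool for comparing a single group with a literature value. On that view only the reference, the margin and the choice of outcome and visit are missing. A protocol often leaves those to a statistical analysis plan, and none is available here. These are also called additional goals and have no hypothesis in Section 7.2, so the wording could be read as loose rather than confirmatory.

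Much of this stands. A reader might infer that the goal cannot be answered at all. The documents do not support that: an analysis plan could name references and margins and use the planned intervals. A reader might also infer that the trial will present significant improvement as non-inferiority. No section says so; Section 10.2 does not link that test to the goal. Nor do the documents support multiplying scales, visits and comparators into a count of false claims. No such set of tests is planned, and the Imperial Score is online only and is not collected at sites outside the UK (Section 11.5). Finally, the importance stated in Section 8.1.3 attaches to the secondary endpoints as a whole, including complications, toxicology and CT migration, and not to these outcomes alone.

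The reply does not remove the mismatch. The protocol itself fixes an aim to demonstrate non-inferiority, has no comparator group, and names as its only test for these outcomes one of a different question. The conflicts over comparator and visits lie within the protocol, and a separate plan would inherit them.

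**Conclusion.** The concern holds in a limited form. The analysis this protocol states cannot answer the goal of demonstrating non-inferiority on patient-reported, functional and radiological outcomes. The comparators differ between the synopsis and Section 7.1.2, and the visits do not fit the schedule for radiographs or gait. This rests on the text alone and on no assumed SD; the power figures above are illustrative. It limits what may be concluded from a secondary goal. It does not touch the test on revision or the metal-ion comparison. It should be corrected, because the present wording promises a conclusion that the stated methods do not deliver.

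**What to change.** In the synopsis and Section 7.1.2, restate the goal as describing these outcomes, with the 95% confidence intervals already planned in Section 10.2, alongside published results for the named comparator or comparators. If a non-inferiority claim is wanted, limit it to one named scale at one visit, tested by a confidence bound against a stated reference value and margin, each with its source.

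In either case:
- state in Section 10.2 that the tests of improvement do not support a non-inferiority conclusion;
- make the synopsis and Section 7.1.2 name the same comparator or comparators;
- replace the reference to every follow-up visit with the visits at which each outcome is scheduled.

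The descriptive option changes wording only; no procedure, visit or sample size changes. The price is that a secondary goal becomes descriptive or narrower. A retained claim would also need a check that the evaluable number suffices for the chosen margin.
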